7.1.2 Part 2 Study Treatment Administration

Starting 6 weeks after the last co-administered dose in Part 1, participants will be administered a flat dose 480 mg nivolumab 30-minute infusion every 4 weeks (Q4W) until unacceptable toxicity or disease progression is reached, whichever comes first.

Participants may be dosed up to 3 days after the scheduled date if necessary. Subsequent dosing should be based on the actual date of administration of the previous dose of drug. Every effort should be made to adhere to protocol treatment schedule of administration of nivolumab every 4 weeks in the maintenance phase. In extenuating circumstances in which the participant cannot make the dosing schedule within the 3-day window, BMS Medical Monitor should be contacted.

Note: Subjects who advance to Part 2 will be treated until progression or unacceptable toxicity, whichever comes first.

For details on prepared drug storage, preparation, and administration, please refer to the nivolumab, ipilimumab and BMS-986237 IBs and/or pharmacy reference sheets. The selection and timing of dose for each participant is as follows:

7.1.3 Selection and Timing of Dose

Table 7.1.3-1: Selection and Timing of Dose Part 1 (Arm A) (Administered as one 60-minute infusion, every 3 weeks for up to 4 doses).

Study Treatment	Unit dose strength(s)/Dosage level(s)	Dosage formulation Frequency of Administration	Route of Administration
BMS-986237	4 mg/kg	Every 3 Weeks (4 total doses)	IV

Table 7.1.3-2: Selection and Timing of Dose Part 1 (Arm B) - (Administered sequentially within the same day, as two separate infusions, one 60-minute nivolumab infusion and one 30-minute ipilimumab infusion with a 30 minute break between each infusion, every 3 weeks for up to 4 doses)

Study Treatment	Unit dose strength(s)/Dosage level(s)	Dosage formulation Frequency of Administration	Route of Administration
nivolumab	3 mg/kg	Every 3 Weeks (4 total doses)	IV
ipilimumab	1 mg/kg	Every 3 Weeks (4 total doses)	IV

Table 7.1.3-3: Selection and Timing of Dose Part 2 (All Participants) - (Administered as infusion over 30 minutes every four weeks in Part 2 until progression or unacceptable toxicity)

Study Treatment	Unit dose strength(s)/Dosage level(s)	Dosage formulation Frequency of Administration	Route of Administration
nivolumab	480 mg	Every 4 weeks	IV

When nivolumab and ipilimumab are to be administered on the same day, nivolumab is to be administered first. Nivolumab infusion must be promptly followed by a saline flush to clear the line of nivolumab before starting the ipilimumab infusion. The second infusion will always be the ipilimumab study treatment and will start after the infusion line has been flushed, filters changed and participant has been observed to ensure no infusion reaction has occurred. The time in between infusions is expected to be approximately 30 minutes but may be more or less depending on the situation.

There will be no dose escalations or reductions of study treatment allowed. For Q4W dosing cycles, participants may be dosed within a \pm 3-day window. Premedications are not recommended for the first dose of nivolumab.

Participants should be carefully monitored for infusion reactions during study treatment administration. If an acute infusion reaction is noted, participants should be managed according to [Section 7.4.5](#).

Doses of nivolumab, ipilimumab, and BMS-986237 may be interrupted, delayed, or discontinued depending on how well the participant tolerates the treatment. Dosing visits are not skipped, only delayed.

Nivolumab injection is to be administered as a ~ 60-minute IV infusion through a 0.2-micron to 1.2-micron pore size, low-protein binding (polyethersulfone membrane) in-line filter at the

protocol specified doses and infusion times. It is not to be administered as an IV push or bolus injection. Nivolumab injection can be infused undiluted (10 mg/mL) or diluted with 0.9% Sodium Chloride Injection, USP or 5% Dextrose Injection, USP to protein concentrations as low as 0.35 mg/mL. During drug product preparation and handling, vigorous mixing or shaking is to be avoided. Instructions for dilution and infusion of nivolumab injection are provided in the clinical protocol, pharmacy binder, pharmacy manual, or pharmacy reference sheet. Care must be taken to assure sterility of the prepared solution as the product does not contain any antimicrobial preservative or bacteriostatic agent. Nivolumab infusions are compatible with polyvinyl chloride (PVC) or polyolefin containers and infusion sets, and glass bottles. Vials of nivolumab injection must be stored at 2°C to 8°C (36°F to 46°F) and protected from light and freezing.

Ipilimumab injection can be used for IV administration without dilution after transferring to a PVC, non-PVC/non-DEHP or glass container and is stable for 24 hours at 2° - 8°C or room temperature/room light (RT/RL). For ipilimumab storage instructions, refer to ipilimumab IB and/or pharmacy reference sheets.

Separate infusion bags and filters should be used when administering nivolumab and ipilimumab on the same day.

Ipilimumab is to be administered as a ~30 minute IV infusion, using a volumetric pump with a 0.2 to 1.2 micron in-line filter at the protocol-specified dose. The drug can be diluted with 0.9% normal saline or 5% Dextrose Injection to concentrations between 1 mg/mL and 4 mg/mL. It is not to be administered as an IV push or bolus injections. Care must be taken to assure sterility of the prepared solutions, since the drug product does not contain any antimicrobial preservatives or bacteriostatic agents. At the end of the infusion, flush the line with a sufficient quantity of normal saline or 5% dextrose solution.

BMS-986237 injection is to be administered as an IV infusion through a 0.2-micron pore size, low-protein binding in-line filter at the protocol-specified doses and infusion times. It is not to be administered as an IV push or bolus injection. Prior to infusion, the BMS-986237 injection is diluted with 0.9% Sodium Chloride Injection, United States Pharmacopeia (USP) to required concentrations.

BMS-986237 is available as a solution at a concentration of 11.4 mg/mL. The volume for calculated weight based dose (refer to pharmacy reference sheets) is to be added to 40 mL of 0.9% Sodium Chloride (normal saline) USP prior to being administered to the participant as an infusion, at a flow rate of less than or equal to 2.5 mL/min over ~ 60 minutes.

During drug product preparation and handling, vigorous mixing or shaking is to be avoided. Vials of BMS-986237 injection must be stored at 2° to 8°C (36° to 46°F) protected from light and it must not be frozen. Further instructions for dilution and infusion of BMS-986237 injection are provided in the clinical protocol, pharmacy binder, or pharmacy reference sheet. Care must be taken to assure sterility of the prepared solution as the product does not contain any antimicrobial preservative or bacteriostatic agent. No incompatibilities between BMS-986237 and polyvinyl chloride (PVC) and polyolefin containers/IV components have been observed.

7.2 Method of Treatment Assignment

All participants will be centrally randomized or using an Interactive Response Technology (IRT). Before the study is initiated, each user will receive log in information and directions on how to access the IRT.

Once enrolled in IRT, enrolled subjects that have met all eligibility criteria will be ready to be randomized through the IRT. The following information is required for subject randomization:

- Subject number
- Date of birth
- IMDC prognostic score at screening (0 vs 1-2 vs 3-6)

Subjects meeting all eligibility criteria will be randomized in a 1:1 ratio to Arm A or Arm B, stratified by IMDC prognostic score. The randomization procedures will be carried out via permuted blocks within each stratum. The exact procedures for using the IRT will be detailed in the IRT manual.

Study treatment will be dispensed at the study visits as listed in Schedule of Activities ([Section 2](#)).

7.3 Blinding

This is an open-label study; however, the specific treatment to be taken by a participant will be assigned using an Interactive Response Technology (IRT). The site will contact the Interactive Response System prior to the start of study treatment administration for each participant. The site will record the treatment assignment on the applicable case report form, if required.

7.4 Dosage Modification

7.4.1 Dose Delay Criteria

Regardless of whether or not the event is attributed to nivolumab, ipilimumab, or BMS-986237, all study treatments must be delayed until treatment can resume. Tumor assessments for all participants should continue as per protocol even if dosing is delayed.

Nivolumab, ipilimumab, and BMS-986237 administration should be delayed for the following:

- Grade 2 non-skin, drug-related adverse event, with the exception of fatigue
- Grade 2 drug-related creatinine, AST, ALT and/or Total Bilirubin abnormalities
- Grade 3 skin, drug-related adverse event
- Grade 3 drug-related laboratory abnormality, with the following exceptions:
 - Grade 3 lymphopenia or asymptomatic amylase or lipase does not require dose delay
 - Grade ≥ 3 AST, ALT, Total Bilirubin will require dose discontinuation (see [Section 7.4.3](#))
- Any adverse event, laboratory abnormality, or intercurrent illness which, in the judgment of the investigator, warrants delaying the dose of study medication.

Participants who require delay of study treatment should be re-evaluated weekly or more frequently if clinically indicated and resume study treatment dosing when re-treatment criteria are met.

7.4.2 Criteria to Resume Treatment

Participants may resume treatment with study treatment when the drug-related AE(s) resolve to Grade \leq 1 or baseline value, with the following exceptions:

- Participants may resume treatment in the presence of Grade 2 fatigue
- Participants who have not experienced a Grade 3 drug-related skin AE may resume treatment in the presence of Grade 2 skin toxicity
- For participants with Grade 2 AST, ALT and/or Total Bilirubin abnormalities, dosing may resume when laboratory values return to baseline and management with corticosteroids, if needed, is complete.
- Participants with combined Grade 2 AST/ALT AND total bilirubin values meeting discontinuation parameters (Section 7.4.3) should have treatment permanently discontinued.
- Drug-related pulmonary toxicity, diarrhea or colitis or myocarditis myositis, rhabdomyolysis must have resolved to baseline before treatment is resumed. Participants with persistent Grade 1 pneumonitis after completion of a steroid taper over at least 1 month may be eligible for retreatment if discussed with and approved by BMS Medical Monitor.

Participants with drug-related endocrinopathies adequately controlled with only physiologic hormone replacement may resume treatment after consultation with the BMS Medical Monitor. Adrenal insufficiency requires discontinuation regardless of control with hormone replacement.

7.4.3 Dose Discontinuation

The assessment for discontinuation of nivolumab should be made separately from the assessment made for discontinuation of ipilimumab. Although there is overlap among the discontinuation criteria, if discontinuation criteria are met for ipilimumab but not for nivolumab, treatment with nivolumab may continue if ipilimumab is discontinued. In this instance, the patient would be considered off part 1 of the study and must have a 6 weeks interval before moving on to part 2 of the study (nivolumab monotherapy).

If a participant in any of the nivolumab/ipilimumab combination arms meets criteria for discontinuation and investigator is unable to determine whether the event is related to both or one study drug, the participant should discontinue both nivolumab and ipilimumab and be taken off the treatment phase of the study.

Study treatment should be permanently discontinued for the following:

- Any Grade 2 drug-related uveitis, eye pain or blurred vision that does not respond to topical therapy and does not improve to Grade 1 severity within the re-treatment period OR requires systemic treatment
- Any Grade 3 non-skin, drug-related adverse event lasting $>$ 7 days, or recurs with the following exceptions for laboratory abnormalities, diarrhea, colitis, neurologic toxicity, drug-related

uveitis, pneumonitis, bronchospasm, myositis, myocarditis, rhabdomyolysis, hypersensitivity reactions, infusion reactions, and endocrinopathies:

- Grade 3 drug-related, diarrhea, colitis, neurologic toxicity, uveitis, pneumonitis, bronchospasm, myositis, myocarditis, rhabdomyolysis, hypersensitivity reaction, or infusion reaction of any duration requires discontinuation
- Grade 3 drug-related endocrinopathies, adequately controlled with only physiologic hormone replacement do not require discontinuation. Adrenal insufficiency requires discontinuation regardless of control with hormone replacement.
- Grade 3 drug-related laboratory abnormalities do not require treatment discontinuation except:
 - ◆ Grade 3 drug-related thrombocytopenia > 7 days or associated with bleeding requires discontinuation
 - ◆ Any drug-related liver function test (LFT) abnormality that meets the following criteria requires discontinuation:
 - Grade \geq 3 drug-related AST, ALT or Total Bilirubin requires discontinuation*
 - Concurrent AST or ALT > 3 x ULN and total bilirubin > 2x ULN

* In most cases of Grade 3 AST or ALT elevation, study treatment(s) will be permanently discontinued. If the investigator determines a possible favorable benefit/risk ratio that warrants continuation of study treatment(s), a discussion between the investigator and the BMS Medical Monitor/designee must occur.

- Any Grade 4 drug-related adverse event or laboratory abnormality (including but not limited to creatinine, AST, ALT, or Total Bilirubin).
- Any event that leads to delay in dosing lasting > 6 weeks from the previous dose requires discontinuation, with the following exceptions:
 - Dosing delays to allow for prolonged steroid tapers to manage drug-related adverse events are allowed. However, dosing must be discontinued for any drug related AE that requires treatment with 10mg/day or greater prednisone or equivalent for more than 12 weeks.
 - Dosing delays lasting > 6 weeks from the previous dose that occur for non-drug-related reasons may be allowed if approved by the BMS Medical Monitor.

Prior to re-initiating treatment in a participant with a dosing delay of >6 weeks, the BMS Medical Monitor must be consulted. Tumor assessments should continue as per protocol even if dosing is delayed. Periodic study visits to assess safety and laboratory studies should also continue every 6 weeks or more frequently if clinically indicated during such dosing delays.

Any adverse event, laboratory abnormality, or intercurrent illness which, in the judgment of the Investigator, presents a substantial clinical risk to the participant with continued nivolumab dosing.

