## **7.4.2 Modifications of Study Therapy**

### **7.4.2.1 Dose Delays**

Each nivolumab, ipilimumab, or BMS-986237 infusion may be delayed. A dose will be considered as actually delayed if the delay is exceeding 3 days (ie greater than or equal to 4 days from scheduled dosing date). All studies drugs must be delayed until treatment can resume. Reason for dose delay will be retrieved from CRF dosing pages.

The following parameters will be summarized by treatment group:

- Number of dose delays per subject, length of delay, and reason for delay

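### At the Part 1 to Part 2 transition the 6-week delay limit equals the planned interval, so even a 1-day drug-related delay without a prolonged steroid taper meets the discontinuation rule

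*Protocol*

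**What the plan says.** **The limit.** Protocol 7.4.3 reads: "Any event that leads to delay in dosing lasting > 6 weeks from the previous dose requires discontinuation". There are two exceptions. The first is "Dosing delays to allow for prolonged steroid tapers to manage drug-related adverse events are allowed", subject to a 12-week cap on steroid treatment. The second concerns delays past 6 weeks "that occur for non-drug-related reasons may be allowed if approved by the BMS Medical Monitor". The section then requires the Medical Monitor to be consulted before treatment restarts after a delay of more than 6 weeks.

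**The planned interval.** Protocol 7.1.2 places the first flat nivolumab dose as follows: "Starting 6 weeks after the last co-administered dose in Part 1". Table 2-3 likewise puts Cycle 5 at 6 weeks after Cycle 4. Section 7.4.3 makes 6 weeks a required interval before Part 2 when ipilimumab alone is stopped.

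**The window.** Protocol 7.1.2 adds for Part 2: "Participants may be dosed up to 3 days after the scheduled date if necessary". It asks for Medical Monitor contact only when the dose cannot be given inside the 3-day window.

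**Delay and restart.** Protocol 7.4.1 has dosing held for, among others, Grade 2 drug-related non-skin events other than fatigue, and Grade 2 drug-related creatinine or liver test abnormalities. Protocol 7.4.2 allows dosing again once the event is back to Grade 1 or lower or to baseline, with some exceptions. For Grade 2 liver tests it treats corticosteroids as conditional on need.

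No passage exempts the step from Part 1 to Part 2 from the 6-week limit.

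**The concern.** A limit counted from the previous dose works only if it is longer than the planned gap between doses. That is so within Part 1 and within Part 2. At the transition the two are equal, so an event that holds Cycle 5 at all carries the participant past the limit. Where neither exception applies, the same participant is told to wait, allowed to resume on recovery, and required to stop.

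At stake is who enters Part 2. That choice determines the SAP's Part 2 population, the discontinuation counts and Part 2 exposure. It also moves the last-dose date, which closes the 30-day window for the drug-related and all-causality Grade 3-5 adverse event rates. Later outcomes such as PFS may be affected too. Sites have to settle the conflict themselves, and because the trial is open-label they do so knowing the arm.

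**Working it through.** Days are counted from the previous dose, with the dosing day as day 0.

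**Inputs**
- Discontinuation limit: more than 6 weeks = more than 42 days (Protocol 7.4.3)
- Part 1 interval: 21 days (Protocol Table 2-2)
- Part 2 interval: 28 days (Protocol 7.1.2, Table 2-3)
- Last Part 1 dose to Cycle 5: 42 days (Protocol 7.1.2, Table 2-3)
- Late allowance: 3 days (Protocol 7.1.2)

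**The plan's own calendar.** Cycle 4 falls 3 × 21 = 63 days after Cycle 1. Cycle 5 then falls 63 + 42 = 105 days after Cycle 1. Since 105 / 7 = 15 full weeks, that is the first day of Week 16. The footnote to Table 9.5-1 starts Part 2 at Week 16, so a planned interval of 42 days is what the plan intends.

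**Margin before the limit** = 42 − planned interval. **Latest dose with 3 days' lateness** = planned interval + 3.

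| Step | Planned (days) | Margin (days) | Planned + 3 | Past day 42? |
|---|---|---|---|---|
| Between Part 1 doses | 21 | 42 − 21 = 21 | 24 | No |
| Between Part 2 doses | 28 | 42 − 28 = 14 | 31 | No |
| Last Part 1 dose to Cycle 5 | 42 | 42 − 42 = 0 | 45 | Yes, by 3 days |

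**The case neither exception reaches.** Suppose a participant has a Grade 2 drug-related event, managed without a prolonged steroid taper, that holds the dose for 7 days (an illustration, not a figure from the documents).
- Between Part 1 doses: 21 + 7 = 28 days, inside the limit.
- Between Part 2 doses: 28 + 7 = 35 days, inside the limit.
- At Cycle 5: 42 + 7 = 49 days, past the limit. The taper exception does not apply, and the other exception is for non-drug-related reasons only. Section 7.4.1 required the hold, 7.4.2 allows restart, and 7.4.3 requires discontinuation. The result is the same from day 43 onward.

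**Ipilimumab alone stopped.** Section 7.4.3 does not say where its 6-week interval starts. If it starts at the last Part 1 dose, as in 7.1.2 (an assumption), the earliest permitted Part 2 dose is day 42. The limit for a dose held by an event is also day 42, so only one day satisfies both.

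**The Grade 3-5 window.** If Cycle 5 is never given, the window closes on day 30 after the last Part 1 dose, which is 42 − 30 = 12 days before Cycle 5 was due. If Cycle 5 is given on day 49, the window runs at least to day 49 + 30 = 79.

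**The case against.** **The exceptions are wide.** A reader who stops at the 6-week rule might infer that any lateness at Cycle 5 forces discontinuation. The documents do not support that: steroid-taper delays are allowed and non-drug-related delays may be approved. This part of the objection stands and confines the point to drug-related events without a prolonged taper. The requirement to consult before restart does not add a third exception. It governs restarts that the two exceptions already permit.

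**A dose inside the window may not be a delay.** The rule is triggered by an event that leads to delay, whereas 7.1.2 is a scheduling allowance. A reader might infer a flat contradiction for every dose on days 43 to 45. An ordinary scheduling slip may never trigger 7.4.3, and the text does not say. This stands for scheduling slips. It does not help when the cause is a drug-related event, or from day 46 onward.

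**A uniform ceiling is a legitimate choice.** Everyone gets the same 42 days since last exposure, and unequal margins follow from unequal intervals. That is fair as far as it goes, but it does not explain why 7.4.1 and 7.4.2 provide for a hold and restart that 7.4.3 forbids at this one step.

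**The wording could mean something else.** The consultation sentence speaks of a delay longer than 6 weeks without saying from when. If the delay itself were meant, the limit at Cycle 5 would be 42 + 42 = 84 days. The rule and its second exception both count expressly from the previous dose, so the 42-day reading is the better supported.

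**The consequences are limited.** The primary and first secondary endpoints count events within 2 days of Part 1 infusions, so Cycle 5 timing cannot touch them. The rule is the same in both arms, and SAP 7.1 makes all analyses descriptive. All of this stands.

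**Conclusion.** The point holds in a narrow form. The margin at Cycle 5 is 0 days, against 21 and 14 days elsewhere. A drug-related event managed without a prolonged steroid taper that moves Cycle 5 by even one day meets the discontinuation rule, despite the hold-and-resume path in 7.4.1 and 7.4.2. For days 43 to 45 the protocol does not say which provision governs. This rests on counting the limit from the previous dose, as 7.4.3 says.

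Three further inferences are not supported:
- **A count of affected participants.** The documents give no frequency of such delays. Most of the steroid algorithms in Appendix 8 are figures not available here. The right denominator would be those who proceed towards Part 2, not all 100 treated.
- **An error in the SAP.** SAP 7.4.2.1 says: "A dose will be considered as actually delayed if the delay is exceeding 3 days". That measures lateness against the scheduled date for exposure tables, a different purpose from a stopping limit.
- **A conflict between the two Part 2 windows.** Protocol 7.1.3 gives ±3 days where 7.1.2 gives up to 3 days after. They differ only for early dosing, so the difference does not bear on a late Cycle 5.

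Part 2 entry, exposure, the Grade 3-5 window and possibly later outcomes are affected. The two Grade 3-5 rates are analysed when on-treatment participants have completed Part 1, so they are affected only through participants who reach their Cycle 5 date before that analysis.

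**What to change.** Reconcile Protocol 7.4.3 (both the delay limit and the required interval after ipilimumab alone is stopped) with 7.1.2, so that the limit, the planned 6-week interval and the dosing window can all be followed at the Part 1 to Part 2 transition. The text should say what applies to a drug-related delay without a prolonged steroid taper at Cycle 5, and which provision governs days 43 to 45. The sponsor's clinical team decides which rule stands.

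The cost is a clarifying sentence in a protocol amendment or administrative letter. SAP 7.4.2.1 needs no change.
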